**Mammography**

*The issue of mammography as a potential cause of ruptures will be analyzed using a Cox proportional hazards model of time to rupture with number of mammograms as a time varying covariate. In this model, all ruptures, both symptomatic and silent (identified by MRI), will be included. The number of mammograms will include mammography where a patient has been recalled for re-imaging. The coefficient of the time varying covariate will provide an estimate of the effect, if any, on risk of rupture of each mammogram. By collecting information on the timing of mammography and information concerning the stage of breast cancer upon first diagnosis, an analysis of any potential interference issues also will be performed.*

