### 3.0 DESIGN

This protocol amendment includes participant follow-up only. Study enrollment has been closed since 15 Oct 2008 and no new study participants will be enrolled. Data collection will only take place if a participant requires a secondary procedure/reoperation. There are no longer requirements for scheduled office visits or annual participant questionnaires. The study is currently in year 7 and follow-up will continue through 10 years or until the National Breast Implant Registry opens for data collection, whichever occurs first.

As in the original protocol, there will be no concurrent controls needed as a source of comparison for secondary procedures/reoperations (see local complications category in original study design Tables 1 and 2). Thus, saline implant participants will not have data collected under this amended protocol.

Mentor will employ third party study entities that will be responsible for the following: (1) collecting data from surgeons; (2) entering data into and administering the study database; (3) generating follow-up reports as well as datasets; (4) meeting with Mentor on a regular basis; and (5) analyzing the study data. Mentor will be responsible for: (1) IRB approval; (2) monitoring third party entities; (3) analyzing the study data; and (4) periodic reporting to FDA.

The postapproval study was originally designed as follows:

*MemoryGel™ PAS uses a current cohort design of the first 41,900 women receiving Mentor's MemoryGel implants, with 10 years of follow-up. It will include augmentation, reconstruction, and revision patients, each in their naturally occurring proportions at participating study sites.*

*For the purpose of assessing rheumatological and neurological signs and symptoms, there also will be 1,000 saline breast implant patients from the participating surgeons' practices who will serve as concurrent controls. Concurrent control participants will be enrolled by approximately 30 physicians who routinely use saline implants. These investigative sites will be selected with the objective of obtaining the desired number of controls in an appropriate time frame, e.g. roughly the same time frame as the recruitment of MemoryGel subjects. These sites are to enroll all saline subjects meeting the specified eligibility criteria until 1,000 controls are recruited into this study.*

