### **Eligibility Criteria: Saline Breast Implant Control Participants**

#### **Inclusion Criteria**

To be included in the study, each saline control participant must be a woman who:

1. Is a candidate for breast augmentation and is at least 18 years old (primary or revision) **OR** is a candidate for breast reconstruction (primary or revision) with saline breast implants.
2. Signs an Informed Consent Form and an Authorization to Disclose Health Information and Release Medical Records
3. Completes the baseline questionnaire (as evidenced by the participant's signature on the last page of the questionnaire).
4. Agrees to authorize return of the device(s) to Mentor if they are Mentor devices.
5. Agrees via Informed Consent to comply with study follow-up, including full participation in all follow-up questionnaires and responding to questionnaires in their entirety
6. Is a U.S. resident

---

 Breast augmentation includes primary breast augmentation to increase the breast size, as well as revision surgery to correct or improve the result of an original primary breast augmentation surgery.

 Breast reconstruction includes primary reconstruction to replace breast tissue that has been removed due to cancer or trauma or that has failed to develop properly due to a severe breast abnormality. Breast reconstruction includes revision surgery to correct or improve the result of an original primary breast reconstruction surgery.

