#### Complications/Reoperations

The cumulative incidence of key local complications (explantation, and reoperation) for women with MemoryGel implants will be estimated based on physician evaluations for the MemoryGel participants using Kaplan-Meier methodology to estimate the time to the first occurrence of the complication or reoperation. Ninety-five percent confidence intervals will be computed. In addition, the relative frequency of reasons for reoperation will be computed.

Under the original protocol, the purpose of the inclusion of the saline participants was to serve as concurrent controls for assessing rheumatologic and neurologic signs. Rheumatological and neurological data will not be collected under this protocol amendment.

Mentor will generate the following final clinical study reports for submission to FDA:

- One final report at the end of the study phase conducted under Amendment 1, including data from beginning of the study through the end of the study phase under Amendment 1. The statistical analysis will be conducted as described in the original protocol (see below).
- One final report at the end of the study phase conducted under Amendment 2, including data from the execution of Amendment 2 to the end of the study. The statistical analysis will be conducted as described above.

The original analyses conducted to address each of the postapproval study's original objectives are identified below and correspond to issues outlined in Table 1:

*It is important to recognize that this study is observational. As a result, data from this study can be used only to establish association, not causality, and data should be evaluated within the context of the broader composite of literature relating to these issues. All of the analyses, except for the analyses of rheumatological and neurological signs and symptoms, will be based on the MemoryGel participants only.*

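### The mammography–rupture Cox model pools indications and does not tie mammograms to the implanted breast, so its coefficient may not be the effect of each mammogram, with bias possible in either direction

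*Combined protocol and SAP*

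**What the plan says.** Section 11.1 (Mammography) specifies a "Cox proportional hazards model of time to rupture with number of mammograms as a time varying covariate". On events, it says that "all ruptures, both symptomatic and silent (identified by MRI), will be included". On exposure: "The number of mammograms will include mammography where a patient has been recalled for re-imaging". On interpretation: "The coefficient of the time varying covariate will provide an estimate of the effect, if any, on risk of rupture of each mammogram". It names no other covariate, no stratum, no unit of analysis (woman, breast or implant) and no side.

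The population is set under Complications/Reoperations in the same section: "All of the analyses, except for the analyses of rheumatological and neurological signs and symptoms, will be based on the MemoryGel participants only". Section 3.0 says of the cohort: "It will include augmentation, reconstruction, and revision patients, each in their naturally occurring proportions at participating study sites". Footnote 2 of Section 4.0 says that reconstruction includes "primary reconstruction to replace breast tissue that has been removed due to cancer or trauma". It also covers failed breast development and revision of an earlier reconstruction.

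The analysis is live. Section 11.1 has the Amendment 1 final report follow the original analyses, and mammography is one of the original objectives in Table 1. Elsewhere in Section 11.1 the comparisons with national norms are standardised for age, race and other characteristics, and the signs-and-symptoms comparison is regression-adjusted. Nothing of the kind is written for this model.

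A companion analysis of interference uses the timing of mammography and "information concerning the stage of breast cancer upon first diagnosis". It does not say that the diagnosis must follow implantation.

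**The concern.** A single coefficient can be read as the effect of each mammogram only if two things hold: women with high and low counts would otherwise have similar rupture hazards, and each counted mammogram acts on an implant at risk. The plan secures neither.

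Indication could plausibly be related to how often a woman is imaged, how many implants she has and her rupture hazard. If it is related to both uptake and hazard, it confounds the pooled coefficient. Separately, after one-sided reconstruction some mammograms may be of the other, native breast, yet they would add to the count. At stake is the answer to a named safety objective: a harmful effect could be hidden, or a harm signal could appear where there is none.

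**Working it through.** The plan gives no event count, power or hazard ratio for this analysis, so there is no stated figure to reproduce. It also gives no reconstruction share, uptake, one- or two-sided split, or rupture rate by indication. Every rate below is an assumption.

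**Mechanism, by hand.** Take one year, 20% reconstruction, and relative hazard 1 for augmentation women without a mammogram.

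- *Confounding, no true effect.* Uptake is 30% (augmentation) and 80% (reconstruction). Women with one mammogram: 0.80 × 0.30 = 0.24 augmentation and 0.20 × 0.80 = 0.16 reconstruction. Women with none: 0.56 and 0.04.
  - Reconstruction hazard half: (0.24 + 0.16 × 0.5)/0.40 = 0.80 against (0.56 + 0.04 × 0.5)/0.60 = 0.967, a ratio of 0.83.
  - Reconstruction hazard double: (0.24 + 0.16 × 2)/0.40 = 1.40 against (0.56 + 0.04 × 2)/0.60 = 1.067, a ratio of 1.31.
- *Counted mammograms that miss the implant.* Uptake is 50% in both groups, hazards are equal, the true ratio is 1.10 in augmentation, and no reconstruction mammogram reaches the implant: (0.40 × 1.10 + 0.10 × 1)/0.50 = 1.08 against 1.00. The effect is diluted, not reversed.

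**Ten-year calculation.** The large-sample limit of the pooled Cox coefficient solves the score equation

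Σ over years of [Σ d·m − (Σ d) × Σ(w·m·exp(βm)) / Σ(w·exp(βm))] = 0,

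where m is the cumulative count, w the women at risk with that count and d their expected ruptures. Baseline hazard is 0.5% a year, with at most one mammogram a year, acting on the implant in augmentation only. Entries are for reconstruction shares of 10%, 20% and 30%, with a true ratio of 1.10. The hazard columns give reconstruction relative to augmentation, per woman.

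| Uptake, augmentation/reconstruction | Hazard × 0.5 | Hazard × 1 | Hazard × 2 |
|---|---|---|---|
| 30%/80% | 0.974, 0.925, 0.896 | 1.027, 1.003, 0.990 | 1.117, 1.121, 1.121 |
| 50%/80% | 1.013, 0.958, 0.919 | 1.047, 1.015, 0.994 | 1.109, 1.113, 1.113 |
| 50%/50% | 1.096, 1.091, 1.086 | 1.092, 1.084, 1.076 | 1.086, 1.073, 1.062 |
| 50%/30% | 1.140, 1.173, 1.200 | 1.107, 1.111, 1.112 | 1.051, 1.020, 0.999 |

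The whole grid runs from 0.90 to 1.20. The milder mixes with more imaging in reconstruction women (10% share with either such uptake, or 20% with 50%/80%) run from 0.958 to 1.117, about 0.96 to 1.12. Equal uptake gives 1.06 to 1.10.

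With a true ratio of 1.00, which breast is imaged no longer matters, yet the pooled model reads 0.89 to 1.15. It reads 1.00 whenever uptake or hazard is equal across groups. That spread is confounding by indication alone.

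**Finer mix over seven years.** Rupture hazard is 1% per implant-year. Augmentation women have two imaged implants and 0.5 mammograms a year. Half of reconstruction is one-sided (one implant, native breast imaged, 1.0 a year) and half two-sided (no mammograms). At 10%, 20% and 30% reconstruction:

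- A true 1.10 reads 1.06, 1.03 and 1.00, and a true 1.00 reads 0.98, 0.96 and 0.95.
- With 0.3 and 0.9 mammograms a year, a true 1.10 reads 1.03, 0.99 and about 0.96.
- With 0.5 a year in both imaged groups, it reads 1.10 to 1.08.

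**Remedies.** In the two-group grid, stratifying by indication brings a true 1.10 back to 1.06 to 1.10. In the finer mix at 0.5 and 1.0 mammograms a year, it leaves 1.06 to 1.01: within reconstruction, every woman with a mammogram has one implant (1% a year), while those without include women with two (2% a year). Restricting to augmentation returns 1.10 in both models.

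**The case against.** A reader might infer that the plan counts mammograms per woman, that reconstruction women are imaged on the breast without the implant, and that a real effect must therefore be diluted or turned below 1. The documents do not support that chain. The unit is undefined rather than stated as the woman, and the MRIs paragraph of Section 11.1 classifies rupture by implant. Nothing says which breast is imaged, and footnote 2 covers women to whom the argument need not apply. The direction is not fixed either. With equal uptake, missed mammograms only dilute. Values well below 1 need differences in uptake and hazard by indication as well, and other equally unverified patterns push the coefficient above the truth. If one-sided reconstruction women have the same per-woman hazard as augmentation women, the finer mix shows no reversal. All of this stands.

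Three further points carry weight. Mammography is no longer an Amendment 2 objective, so the reach is limited to one report. Section 11.1 says the data can show association only; that is fair, but it does not excuse leaving out a known and available stratum, and it sits awkwardly with the reading given to the coefficient. Finally, Table 1 asks about the timing of breast cancer diagnosis, which implies cancers found with an implant in place. It would be too strong to say that the stage analysis plans to use cancers that preceded the implant; it only lacks a sentence.

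Stratification alone might look enough and keeps every woman in the model. It removes the bias between indications, but not the bias within reconstruction shown in the finer mix.

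**Conclusion.** The concern holds as a gap in specification with a possible bias of unknown sign. The model pools indications, leaves the exposure unit and side undefined, and adjusts for nothing, while its coefficient is given a per-mammogram meaning. Under the assumed mixes, a true 1.10 can be diluted, pushed below 1 or inflated by the amounts shown above. The loss is small if uptake is equal across indications. These are large-sample limits, so sampling error would come on top.

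The sizes rest wholly on assumed shares, uptake and hazards. The gap itself rests on the text. The documents do not support a forecast that the reported effect will be too low. The change should be made before the Amendment 1 report is analysed. The stage point is a minor clarification.

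**What to change.** In Section 11.1 (Mammography):

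1. Stratify the rupture model by indication and, where recorded, by number of implants (one or two).
2. Report the augmentation-only estimate (primary and revision) as the one read as the per-mammogram effect, with reconstruction shown separately. All MemoryGel women named in the Table 1 objective then remain in the report.
3. State the unit of exposure and event. If the imaged side was recorded, analyse by implanted breast, count only mammograms of that breast, and cluster the variance by woman.
4. As a clarification, limit the stage analysis to breast cancers first diagnosed after implantation.

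The cost is a few sentences. Indication is part of the eligibility criteria in Section 4.0, so items 1 and 2 need no new data beyond the number of implants where it is held. Item 3 depends on what was collected under Amendment 1, which this document does not show. The downside is fewer ruptures and cancers in the estimates to be interpreted, hence slightly wider intervals.

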**MRIs**

*The frequency with which women with MemoryGel implants undergo MRI screening will be examined in three ways. First, the time to first MRI will be examined using the method of Kaplan-Meier. Similarly, the time to second MRI following the first MRI will be examined using the Kaplan-Meier method. Finally, the overall frequency of MRIs will be examined by computation of the ratio of the number of MRIs to the total number of person-years with MemoryGel implants.*

*MRI findings will be utilized in the analysis of overall rupture rates (including both symptomatic ruptures and “silent ruptures” detected by MRI) over time). These data will be analyzed using the method of Kaplan-Meier. In this analysis, both symptomatic ruptures and silent ruptures detected by MRI will be considered ruptures, except that implants with symptomatic and silent ruptures which are explanted and determined on physical examination by Mentor not to have been ruptured will be considered to be intact.*

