Cancer	
 
• What are the types and rates of cancer reported for women receiving Mentor MemoryGel implants and controls?
 

Suicide	
 
• What are the rates of suicide for women receiving Mentor MemoryGel implants and controls?
 

Mammography	
 
• What is the rate of rupture with mammography in women receiving Mentor MemoryGel implants?
 
• Are there interference issues (i.e., is there an effect with respect to the timing of breast cancer diagnosis?)
 

MRI Compliance and Results	
 
• How many women receiving Mentor MemoryGel implants obtained MRIs as described in the patient brochure (i.e., at year 3 and every 2 years, thereafter)? If not this schedule, how often did they get one?
 
• What are the rupture rates based on the MRI findings?
 

 To include (patient-reported key local complications): infection; breast pain; capsular contracture (Baker Grades I-IV); rupture; removal; and reoperation. Physicians will

report all local complications, including reasons for reoperation, with or without removal, and reasons for removal, during scheduled and unscheduled/interim visits (see complications form in Section 15).

-  To include the following diseases diagnosed or reviewed and confirmed by a board-certified rheumatologist; scleroderma, lupus, rheumatoid arthritis, Sjögren's Disease, fibromyalgia, and other CTDs or autoimmune diseases [participant to specify in questionnaire]. Separately, a survey-based evaluation of fibromyalgia, determined through patient reports via a validated instrument that correlates to rheumatologist diagnosis, will be included (Katz, R.S., F. Wolfe and K. Michaud. 2006. Fibromyalgia diagnosis: a comparison of clinical, survey, and American College of Rheumatology criteria. *Arthritis Rheum.* 54(1):169-176).

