## 11.2 Sample Size Determination

Study enrollment has been closed since 15 Oct 2008 and no new study participants will be enrolled.

The sample size for the postapproval study originally was determined in the following manner:

*It is assumed that it is required to have 80% power to be able to detect as statistically significant a relative risk of 2.0 for adverse events that occur, without implants, with a frequency of 2.85 per 100,000. This figure is based on the incidence of scleroderma as reported by Mayes et al. (2003). It is assumed this would be based on a one-sided test conducted at the  $\alpha = 0.05$  level of significance. Based on these specifications, it was determined that approximately 338,000 person-years would be required.*

*Patients are to be followed for 10 years. For purposes of sample size calculation, assuming a follow-up rate of 65% at 10 years and a linear loss to follow-up, there would be an average of 8.075 person-years per participant. Thus, in order to obtain the 338,000 person-years, a total of 41,900 MemoryGel participants would be required.*

*The concurrent control sample size was selected in order to be able to detect a relative risk of 2.0 for MemoryGel participants as compared to control participants, for rheumatologic and neurologic signs and symptoms with a prevalence of approximately 2% among MemoryGel participants. It is assumed this would be based on a one-sided test conducted at the 0.05 level of significance with a power of 80%. Similar combined rheumatologic categories of signs and symptoms from Mentor's existing Core Study of these silicone gel implants all have estimated prevalence of at least 2% after year 2. These data will be analyzed by first computing, for each participant, the proportion of time points in which the participant reports the sign or symptom as being prevalent and then calculating the mean of these participant-level proportions across participants within each group. For purposes of sample size calculation, it is assumed that these means will be compared using a simple test based on the normal approximation.*

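### No planned MRI analysis counts the women who followed the year-3-then-every-2-years schedule, and the three planned summaries cannot be used to derive that count

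*Combined protocol and SAP*

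**What the plan says.** The MRI row of Table 1 (section 2.0) poses two compliance questions. The first is "How many women receiving Mentor MemoryGel implants obtained MRIs as described in the patient brochure (i.e., at year 3 and every 2 years, thereafter". The second follows directly: "If not this schedule, how often did they get one". A further question in that row, on rupture rates, is not at issue here.

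The MRIs part of section 11.1 examines frequency in three ways:

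- "the time to first MRI will be examined using the method of Kaplan-Meier";
- "the time to second MRI following the first MRI will be examined using the Kaplan-Meier method";
- "the overall frequency of MRIs will be examined by computation of the ratio of the number of MRIs to the total number of person-years", counting all time with the implants.

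This is text from the original protocol. Section 11.1 keeps it in force for one purpose: the final report on the Amendment 1 phase is to be analysed as the original protocol describes. Amendment 2 collects only reoperation data, and its own objectives contain no MRI question.

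**The concern.** The first question needs each woman's MRI dates to be compared with her due dates. The analysis text has no due date, no window, no classification of individual women and no analysis of timing after the second MRI. The Amendment 1 report is where this objective has to be met. If the plan is followed exactly, that report will describe MRI use without saying how many women kept to the schedule.

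The pooled rate adds a second difficulty, because a reader may take it as a compliance measure. Its denominator includes the years before any MRI is due, and its value under perfect compliance changes with length of follow-up. A low rate could therefore be read as poor compliance when it is not.

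**Working it through.** The documents give no figure for the MRI analyses, so there is none to reproduce. The planned person-years can be checked, since they feed the denominator.

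**Planned person-years (section 11.2).** "Patients are to be followed for 10 years", "assuming a follow-up rate of 65% at 10 years and a linear loss to follow-up". Linear loss to 65% is 3.5 points a year, so end-of-year retention runs 0.965, 0.930, ..., 0.650. The sum is 8.075, which matches the stated average per participant.

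**Can the three outputs yield the on-schedule count?** Take hypothetical cohorts of 100 women, each followed for 10 years (1,000 person-years). Due years are 3, 5, 7 and 9.

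| Cohort | MRI years | First MRI | First-to-second gap | Rate per person-year | On schedule |
|---|---|---|---|---|---|
| A | all 3, 5, 7, 9 | 3 | 2 | 400/1,000 = 0.40 | 100% |
| B | all 3, 5, 5.5, 6 | 3 | 2 | 400/1,000 = 0.40 | 0% |
| C | half 3, 5, 7, 9; half 3, 5 | 3 | 2 | 300/1,000 = 0.30 | 50% |
| D | all 3, 5, 8.5 | 3 | 2 | 300/1,000 = 0.30 | 0% |

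A and B agree on all three planned outputs, and so do C and D. The on-schedule shares differ completely in the first pair and by half in the second. The result does not need 10 years. Drop the last MRI from A and B and stop at year 7: MRIs at 3, 5, 7 and at 3, 5, 5.5 both give a rate of 3/7 = 0.43 and the same curves, with 100% and 0% on schedule. So the count is not determined by the planned outputs.

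**What does the rate equal under full compliance?** Divide the number of due MRIs reached by the years followed:

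| Years followed | 2 | 3 | 4 | 5 | 6 | 7 | 10 |
|---|---|---|---|---|---|---|---|
| Due MRIs reached | 0 | 1 | 1 | 2 | 2 | 3 | 4 |
| Rate | 0 | 0.33 | 0.25 | 0.40 | 0.33 | 0.43 | 0.40 |

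**With the planned retention.** Person-years in years 1-3 are 0.965 + 0.930 + 0.895 = 2.79, and 2.79/8.075 = 34.6% of the total. Full compliance gives 0.895 + 0.825 + 0.755 + 0.685 = 3.16 MRIs per woman. That is 3.16/8.075 = 0.39 per person-year overall, and 3.16/(8.075 - 2.79) = 0.60 over time after year 3.

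**With the reported follow-up.** Sections 1.0 and 4.0 give a MemoryGel follow-up rate of 21.8% through six years. The documents do not define that rate. Assume it is the share still contributing person-years, with linear loss, S(t) = 1 - 0.782t/6:

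- S(3) = 0.609 and S(5) = 0.348, so full compliance gives 0.957 MRIs per woman;
- person-years to year 6 = 6 × (1 + 0.218)/2 = 3.654;
- rate = 0.957/3.654 = 0.26. Exponential loss to the same 21.8% gives 0.24.

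With no loss over the same six years, the rate is 2/6 = 0.33.

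**The case against.** The strongest reply is that the schedule has two elements, a first MRI at year 3 and a 2-year interval, and that the two curves address exactly these. Read near year 3 and near a 2-year gap, they show when the first two MRIs occurred, with censoring handled. An MRI in the first year would appear as an early step. That stands as description. But the curves are separate summaries: they do not link a woman's first date to her own later gap, and they stop at the second MRI. They can limit the share compliant at year 3 but cannot count the women on schedule.

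The second reply is that the rate was meant for the question of how often, where total implant time is a legitimate denominator. That also stands, although the answer is pooled over all women and not confined to those off schedule. A reader might infer that the whole compliance objective goes unanswered. The documents do not support that: the first question is unanswered and the second is answered in pooled form.

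Three other inferences go too far.

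- **The rate mainly reflects drop-out.** Under the assumed linear loss, drop-out moves it from 0.33 to 0.26 over six years. The 3-year lead-in and the cut-off at year 6 already separate 0.33 from the 0.50 implied by a 2-year interval.
- **Symptom-driven MRIs are counted as screening.** The text gives no rule either way, and section 9.0 refers to Amendment 1 for the survey data-collection details.
- **The same data would support opposite conclusions because the overall rate can coincide.** Where full compliance is set against purely diagnostic MRIs, the first-MRI curve would normally differ, and the plan reports all three outputs.

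The analysis is also descriptive, has no control group and plays no part in the sample size. This limits the consequence of the gap but does not close it.

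**Conclusion.** The point holds in this form: the number of women on the brochure schedule is a stated question with no planned analysis, and the three planned summaries cannot supply it. The cohort comparison needs no assumption about the actual data, since it shows only that identical outputs are compatible with 100% and 0% on schedule.

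The pooled rate is acceptable for frequency but has no fixed compliance benchmark. Full compliance reads 0.25, 0.33 or 0.40 at 4, 6 or 10 years of follow-up. It reads about 0.24 to 0.26 if the 21.8% figure means exponential or linear loss, an interpretation the documents do not confirm. The point affects the Amendment 1 final report only. It merits a change because a stated objective is otherwise missed and the remedy is small.

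**What to change.** For the Amendment 1 final report, add one table to the MRIs part of section 11.1.

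- At each due year reached (3, 5 and 7, as far as Amendment 1 follow-up extends), give the number and percent of women with an MRI within a pre-stated window. The denominator is women who still have the implant and whose follow-up covers the window.
- Give the percent compliant at all due times reached.
- Report how many women are excluded for lack of later contact, and add a sensitivity analysis, for example counting them as without an MRI. Women who keep responding may also be likelier to have MRIs, so conditioning on later contact may bias compliance upward.
- Keep both Kaplan-Meier curves and the total person-year rate for the question of how often.
- If a rate from the opening of the first due window is added, restrict its numerator to MRIs in that same time. State the start point: under the linear-loss assumption, full compliance gives about 0.61 from year 2.5 and about 0.50 from year 2.

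The cost is analysis-plan wording and one table. MRI dates are already needed for the curves, so no new data collection is implied. The downsides are that a window must be chosen, as the documents give none, and that precision falls at later due dates.
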